2.2 Study Design and Procedures

2.2.1 Study Design

The study is a randomized, double-blind pilot trial comparing rTMS with sham treatment in reducing stimulant use among individuals with CUD or MUD. Eligible and interested participants will be randomized on a 1:1 ratio to one of two groups; groups will receive up to 30 sessions of active rTMS or sham over the course of an 8-week treatment period.

Four study sites will participate in the study. Each study site will aim to enroll approximately 40 (20 for each of CUD and MUD) participants, with the goal of randomizing 160 (80 for each of CUD and MUD) participants total.

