2.2.4 Randomization

Following determination of full study eligibility via screening, participants will be randomly assigned to one of the two conditions (active rTMS or sham) for 8 weeks of treatment. Random assignment will be on a 1:1 ratio to one of the two conditions. Randomization will be stratified based on study site, presence/absence of current major depressive episode (MDE), and whether the participant enters on primary substance of use CUD or MUD. The sample size within each of CUD and MUD is assumed to be 80. The randomization procedure will be conducted centrally through the DSC, and randomization assignments will not be conveyed to research staff (including rTMS Operators) or participants. The unblinded DSC statistician will generate the randomization

schedule using balanced blocks of varying sizes within strata to ensure lack of predictability along with relative equality of assignments across treatment groups. The unblinded DSC statistician will review randomization data on a regular basis to ensure that the scheme is being implemented according to plan. A randomization slot, once used, will not be re-allocated due to the intent-to-treat (ITT) nature of the study. Further details can be found in the Randomization Plan.

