8.5 Suicide Risk

8.5.1 Self-Reported

The CHRT-SR (CHP) form is a self-reported assessment of suicidality and related thoughts and behaviors (Trivedi et al., 2011) assessed at screening, weekly during the treatment period, and at follow-up visits. Participants reporting suicide ideation/intent is defined as answering “Agree” or “Strongly Agree” on any of the Concise Health Risk Tracking – Participant Rated (CHRT-SR) questions 14, 15 or 16: “I have been having thoughts of killing myself”, “I have thoughts about how I might kill myself” or “I have a plan to kill myself.” The number and percentage of randomized participants with suicide ideation/intent will be summarized by presence or absence of current MDE assessed at baseline, study period, treatment arm, and overall.

A detailed listing for all visits for randomized participants who report suicide ideation/intent at any visit will be provided by treatment arm. The listing will include site, participant ID, date of randomization, presence or absence of current MDE assessed at baseline, visit, date of assessment, and responses to the suicide risk questions.

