17.1.5 Supportive Analyses of the Primary Outcome

Table 35: Summary of Primary Outcome by Sex					
Subgroup	Number of Participants Randomized	Number of Sessions Performed Per Participant ¹ Mean (SD)	Results ³		
			Number of Participants with at Least 20 Sessions ^{1,2} N (%)	95% Lower Confidence Limit	95% Upper Confidence Limit
Male	N	X.X (X.XX)	N (XX.X%)	XX.XX%	XX.XX%
Female					

¹ A rTMS or sham session was considered performed if indicated as such on the rTMS Intervention (TMS) form.

² Percentage is calculated out of the total number of participants randomized.

³ Results are obtained by the Wilson method within the subgroup.

Table 36: Summary of Primary Outcome by Race					
Subgroup	Number of Participants Randomized	Number of Sessions Performed Per Participant ¹ Mean (SD)	Results ³		
			Number of Participants with at Least 20 Sessions ^{1,2} N (%)	95% Lower Confidence Limit	95% Upper Confidence Limit
Black	N	X.X (X.XX)	N (XX.X%)	XX.XX%	XX.XX%
White					
Other ⁴					

¹ A rTMS or sham session was considered performed if indicated as such on the rTMS Intervention (TMS) form.

² Percentage is calculated out of the total number of participants randomized.

³ Results are obtained by the Wilson method within the subgroup.

⁴ Other includes American Indian or Alaska Native, Native Hawaiian or Pacific Islander, Other, and Multiple Race. Missing or refused responses are not included in the analysis (N=X).

Table 37: Summary of Primary Outcome by Ethnicity					
Subgroup	Number of Participants Randomized	Number of Sessions Performed Per Participant ¹ Mean (SD)	Results ³		
			Number of Participants with at Least 20 Sessions ^{1,2} N (%)	95% Lower Confidence Limit	95% Upper Confidence Limit
Not Hispanic or Latinx	N	X.X (X.XX)	N (XX.X%)	XX.XX%	XX.XX%
Hispanic or Latinx					

¹ A rTMS or sham session was considered performed if indicated as such on the rTMS Intervention (TMS) form.

² Percentage is calculated out of the total number of participants randomized.

³ Results are obtained by the Wilson method within the subgroup.

Table 38: Summary of Primary Outcome by Age

Subgroup	Number of Participants Randomized	Number of Sessions Performed Per Participant ¹ Mean (SD)	Results ³		
			Number of Participants with at Least 20 Sessions ^{1,2} N (%)	95% Lower Confidence Limit	95% Lower Confidence Limit
18-44 years	N	X.X (X.XX)	N (XX.X%)	XX.XX%	XX.XX%
45 years or greater					

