xxxxx	xxxxxxxxxxxxxx	mm/dd/yyyy	mm/dd/yyyy	xxxxxxxxxx	Grade 1 – Mild Grade 2 – Moderate Grade 3 – Severe	None Decreased rTMS/sham "dose" Temporarily stopped rTMS/sham Permanently stopped rTMS/sham	Recovering/ resolving Recovered/ resolved Recovering/ resolved with sequelae Not recovered/ not resolved Fatal Unknown	mm/dd/yyyy	Congenital anomaly or birth defect Persistent or significant disability or incapacity Death Initial or prolonged hospitalization Life threatening Other serious event (Important Medical Event)	xxxxxxxxxx	xxxxxxxxxx

SAEs are highlighted in grey.

Table 69: Summary of CHRT – Participant Rated by Treatment Arm

Major Depressive Episode ¹	Number with suicide ideation/intent on CHRT-SR ^{2,3}	Treatment Arm		Total (N=XX)
		Sham (N=XX)	rTMS (N=XX)	
Absent	During screening	N (X.X%)	N (X.X%)	N (X.X%)
	During treatment period			
	During follow-up period			
Present	During screening			
	During treatment period			
	During follow-up period			
Overall	During screening			
	During treatment period			
	During follow-up period			

¹ Current Major Depressive Episode is assessed via the Mini International Neuropsychiatric Interview at baseline.

² Concise Health Risk Tracking-Participant Rated (CHRT-SR). Suicide ideation/intent on CHRT is defined as a response of "Agree" or "Strongly Agree" on any of CHRT-SR questions 14, 15 or 16: In the past week "I have been having thoughts of killing myself", "I have thoughts about how I might kill myself" or "I have a plan to kill myself".

³ Unique randomized participants with suicidal ideation/intent, at least once during the treatment and/or follow-up period. Denominator is the number randomized.

Listing 5: CHRT¹ Participant Rated by Treatment Arm								
Treatment Arm = Sham								
Site	Participant ID	Date of Randomization	Major Depressive Episode²	Visit	Date of Assessment	I have been having thoughts of killing myself	I have thoughts about how I might kill myself	I have a plan to kill myself
xxxxxxxxxx	xxxxxxxxxxxxxx	mm/dd/yyyy	Absent/ Present	Screening Week 1 A1 Week 1 A2 etc.	mm/dd/yyyy	Strongly Disagree Disagree Neither Agree nor Disagree/ Agree Strongly Agree	Strongly Disagree Disagree Neither Agree nor Disagree Agree Strongly Agree	Strongly Disagree Disagree Neither Agree nor Disagree Agree Strongly Agree

All visits are included for randomized participants who answered, 'Agree' or 'Strongly Agree'. Responses of 'Agree' are highlighted in orange and 'Strongly Agree' are highlighted in red.

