Concise Health Risk Tracking- Clinician Rated Module (CHRT- CR) will be performed by the Medical Clinician only if a participant endorses any of questions 14 -16 on the CHRT-SR as “Agree” or “Strongly agree”. Percentage within the time period is calculated as the number of unique randomized participants with the specified type of suicidal ideation/attempt at least once during the week prior to the visit where the assessment occurs, divided by the number of participants randomized.

¹ Current Major Depressive Episode is assessed via the Mini International Neuropsychiatric Interview at baseline.

Listing 6: CHRT ¹ Clinician Rated by Treatment Arm											
Treatment Arm = Sham											
Site	Participant ID	Date of Randomization	Major Depressive Episode ²	Visit	Date of Assessment	Suicidal Ideation					
						Passive	Active/ Non-specific	Active with Method	Active with Method and Intent	Active with Method, Intent and Plan	
xxxxxxxxxx	xxxxxxxxxx	mm/dd/yyyy	Absent/ Present	Screening Week 1 A1 Week 1 A2 etc.	mm/dd/yyyy	No/Yes	No/Yes	No/Yes	No/Yes	No/Yes	No/Yes

All visits are included for randomized participants who answered, 'Agree' or 'Strongly Agree' to any of the Concise Health Risk Tracking - Participant Rated (CHRT-SR) questions 14, 15 or 16: In the past week "I have been having thoughts of killing myself", "I have thoughts about how I might kill myself" or "I have a plan to kill myself".

¹ Concise Health Risk Tracking – Clinician Rated Module (CHRT-CR) form.

² Current Major Depressive Episode is assessed via the Mini International Neuropsychiatric Interview at baseline.

Listing 6: CHRT ¹ Clinician Rated by Treatment Arm											
Treatment Arm = rTMS											
Site	Participant ID	Date of Randomization	Major Depressive Episode ²	Visit	Date of Assessment	Suicidal Ideation					
						Passive	Active/ Non-specific	Active with Method	Active with Method and Intent	Active with Method, Intent and Plan	
xxxxxxxxxx	xxxxxxxxxx	mm/dd/yyyy	Absent/ Present	Screening Week 1 A1 Week 1 A2 etc.	mm/dd/yyyy	No/Yes	No/Yes	No/Yes	No/Yes	No/Yes	No/Yes

All visits are included for randomized participants who answered, 'Agree' or 'Strongly Agree' to any of the Concise Health Risk Tracking - Participant Rated (CHRT-SR) questions 14, 15 or 16: In the past week "I have been having thoughts of killing myself", "I have thoughts about how I might kill myself" or "I have a plan to kill myself".

¹ Concise Health Risk Tracking – Clinician Rated Module (CHRT-CR) form.

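### SAP Tables 69 and 70 split suicidality by baseline MDE but divide by the number randomized, so as written the MDE rows show shares of the arm and not rates within MDE level

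*SAP*

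**What the plan says.** SAP section 8.5.1 asks for the number and percentage of randomized participants with self-reported suicidal ideation or intent, which "will be summarized by presence or absence of current MDE assessed at baseline, study period, treatment arm, and overall". Section 8.5.2 asks for the same breakdown of the clinician-rated categories.

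The shells in SAP section 17.1.8 implement this. Table 69 (CHRT-SR) and Table 70 (CHRT-CR) each have blocks for MDE absent, MDE present and Overall. Within each block there are rows for screening, treatment and follow-up. The columns are Sham, rTMS and Total, and N appears only in those column headers.

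The counting rule is in the footnotes. Table 69, footnote 3, defines the numerator as "Unique randomized participants with suicidal ideation/intent, at least once during the treatment and/or follow-up period" and then states: "Denominator is the number randomized". The Table 70 footnote says that the count is "divided by the number of participants randomized". Neither footnote limits the denominator to the MDE level of the row.

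**The concern.** The reason to split a safety table by MDE is to show the risk in each group. MDE is a randomization stratum, and Protocol section 4.2 explains why: rTMS is an approved treatment for major depressive disorder. Protocol section 4.3.5 lists worsening mood as a potential risk, and SAP section 11.2.1 includes suicide risk in the safety looks for the DSMB.

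A percentage with the whole arm beneath it does not answer that question. It mixes how common MDE is in the arm with how often participants with MDE report suicidality. A reader who takes the MDE-present figure as the rate among depressed participants will read it too low. A reader who compares the present and absent blocks will see a contrast that depends partly on the MDE share.

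**Working it through.** The plan gives no rate for this point, so there is no figure to reproduce. The check is arithmetic on the stated denominator.

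**Inputs**
- Planned size: SAP section 2.2.1, "with the goal of randomizing 160 (80 for each of CUD and MUD) participants total".
- Allocation: SAP section 2.2.4, "Random assignment will be on a 1:1 ratio to one of the two conditions". So n_arm = 160/2 = 80.
- q, the share of the arm with current MDE: not in the documents. It is assumed here over 0.20 to 0.60.

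**Formulas.** Let x be the count in an MDE-present cell.
- Percentage as written: x / n_arm.
- Rate within MDE level: x / (q × n_arm).
- Understatement, MDE present: 1/q.
- Understatement, MDE absent: 1/(1-q).
- Displayed present/absent ratio: true ratio × q/(1-q).

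The factors depend on q and not on n_arm, so they hold whatever the final enrolment.

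| Assumed q | MDE-present N of 80 | Present understated by | Absent understated by | True present/absent ratio of 4 is shown as |
|---|---|---|---|---|
| 0.20 | 16 | 5.0 | 1.25 | 1.00 |
| 0.25 | 20 | 4.0 | 1.33 | 1.33 |
| 0.30 | 24 | 3.3 | 1.43 | 1.71 |
| 0.40 | 32 | 2.5 | 1.67 | 2.67 |
| 0.50 | 40 | 2.0 | 2.00 | 4.00 |
| 0.60 | 48 | 1.7 | 2.50 | 6.00 |

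**Worked example (counts assumed), q = 0.25.** Four of 20 with MDE is 20%, and 3 of 60 without is 5%, a ratio of 4. As written, the cells print 4/80 = 5.0% and 3/80 = 3.8%, a ratio of 4/3 = 1.33.

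**Between arms.** The displayed rTMS/sham ratio in the MDE-present rows is the true ratio × q_rTMS/q_sham. With equal q, a true ratio of 2 is shown as 2. With q of 0.25 on rTMS and 0.20 on sham, it is shown as 2 × 0.25/0.20 = 2.5.

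**Comparison with other shells.** Tables 35-42 and 44 carry a similarly loose footnote ("Percentage is calculated out of the total number of participants randomized"). There, each row has its own count of participants randomized, and another footnote places the interval within the subgroup. The code in section 7.3.1 filters on the subgroup, and section 7.3.2 refers to similar code. Tables 69 and 70 have none of these safeguards. Where the SAP wants a restricted denominator it can say so: Table 6 names the arm at the site, and Table 48 names those with a UDS that week within the substance group.

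**The case against.** The best defence is that the footnotes are shorthand. The SAP uses similar wording in Tables 35-42 and 44 and clearly means the row's subgroup there, and section 8.5 does not itself require a whole-arm denominator. So the authors may have intended the stratum. That is possible, but it does not rescue the shells: a programmer working from Tables 69 and 70 has only the arm and Total Ns to divide by.

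Several limits on the harm do stand. Every cell prints a count, and Table 6 gives MDE counts by arm, so the within-level rate can be rebuilt. Listings 5 and 6 show MDE status for each participant who endorses suicidality. Stratified blocks should keep q similar across arms, which leaves the rTMS/sham ratio roughly intact. The tables are descriptive, with no test attached.

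A reader might infer that the MDE-present rate is understated several-fold, or that the two MDE blocks will look nearly equal. The documents support neither as a fact, because no section gives MDE prevalence. At q = 0.60 the understatement is 1.7-fold, and above q = 0.50 the present/absent contrast is exaggerated rather than flattened.

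A reader might also infer that the follow-up rows are wrong because they keep participants with no CHRT in that period. That is a trade-off and not an error. The number randomized is the convention in the SAP's AE, SAE and device-event summary tables, and restricting to those assessed conditions on retention after randomization.

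**Conclusion.** Wrong as written. The denominator rule in Tables 69 and 70, applied to the shells as drawn, prints a share of the arm in rows that a reader will take as rates by MDE level. The direction is certain on that reading whenever q is below 1. The size is not: it is 5-fold to 1.7-fold for the MDE-present rows if q is 0.20 to 0.60, and that range is an assumption. The present/absent contrast is correct only at q = 0.5, where both rates are halved. The comparison of active with sham is unaffected if q is equal in both arms, and the Overall rows are free of the MDE problem. The wording of the primary-outcome subgroup tables needs no change on this account.

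**What to change.** In Tables 69 and 70:
1. Change the denominator to participants randomized in that arm and MDE level, keeping the whole arm for the Overall rows. In the Total column, use both arms combined in the same way.
2. Show N for each MDE level and arm.
3. Print n/N with the percentage in each cell.
4. As a supplementary display, give the number with at least one CHRT-SR in each period. This should sit beside the randomized denominator and not replace it. It must name CHRT-SR: under Protocol section 12.6.5 the CHRT-CR is completed only after items 14-16 of the CHRT-SR are endorsed, so counting CHRT-CR forms would reduce the denominator to endorsers.

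The cost is footnote and shell edits with the matching table programming. No new data or modelling is needed, since the stratum counts are already planned for Table 6.

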17.1.9 Data Quality

Table 71: Summary of Data Audits				
Site	Date of Audit	Total Fields Audited¹	Total Data Discrepancies²	Error Rate
Site 1	mm/dd/yyyy	N	N	X.XX%
	Subtotal			
Site 2				
Site 3				
Site 4				
Total				

¹ Fields reviewed at monitoring visit comparing the database to source documentation.

² Fields discrepant between database and source documentation.

17.1.10 Protocol Deviations

Table 72: Summary of Protocol Deviations

	Site 1	Site 2	Site 3	Total
Total number of protocol deviations	N			
Number of participants impacted per protocol deviation				
None	N (X.X%)			
One				
More than one				
Total number of major protocol deviations	N			
Type of major protocol deviation				
No consent/assent obtained	N (X.X%)			
Unauthorized assessments and/or procedures conducted prior to obtaining informed consent/assent				
Non-IRB approved/outdated/obsolete informed consent/assent documents used				
Ineligible participant randomized/inclusion/exclusion criteria not met or eligibility not fully assessed prior to randomization				
Study assessments/procedures not followed in accordance with the study protocol				
Inappropriate unblinding				
AE not reported				
SAE not reported				
AE/SAE reported out of protocol specified reporting timeframe				
AE/SAE not elicited, observed and/or documented as per protocol				
Safety assessment (e.g., labs, ECG, clinical referral to care) not conducted per protocol				
Stratification error				
Participant use of protocol prohibited medication				
Study behavioral intervention was not provided/performed as per protocol				
Study devices dispensed to ineligible participant				
Destruction of study materials without prior authorization from sponsor				
Breach of Confidentiality				
Other informed consent/assent procedures issues				
Other inclusion/exclusion criteria issues				
Other laboratory assessments issues				
Other study procedures/assessments issues				
Other adverse events issues				
Other randomization procedures issues				

Table 72: Summary of Protocol Deviations

	Site 1	Site 2	Site 3	Total
Other study behavioral intervention issues				
Other study device issues				
Other significant deviations issues				
Total number of minor protocol deviations	N			
Type of minor protocol deviation				
No consent/assent obtained				
Unauthorized assessments and/or procedures conducted prior to obtaining informed consent/assent				
Non-IRB approved/obsolete informed consent/assent documents used				
Ineligible participant randomized/inclusion/exclusion criteria not met or eligibility not fully assessed prior to randomization				
Study assessments/procedures not followed in accordance with the study protocol				
Inappropriate unblinding				
AE not reported				
SAE not reported				
AE/SAE reported out of protocol specified reporting timeframe				
AE/SAE not elicited, observed and/or documented as per protocol				
Safety assessment (e.g. labs, ECG, clinical referral to care) not conducted per protocol				
Stratification error				
Participant use of protocol prohibited medication				
Study behavioral intervention was not provided/performed as per protocol				
Study devices dispensed to ineligible participant				
Destruction of study materials without prior authorization from sponsor				
Breach of Confidentiality				
Other informed consent/assent procedures issues				
Other inclusion/exclusion criteria issues				
Other laboratory assessments issues				
Other study procedures/assessments issues				
Other adverse events issues				
Other randomization procedures issues				
Other study behavioral intervention issues				
Other study device issues				
Other significant deviations issues				

Listing 9: Protocol Deviations												
Deviation Category = Category Name 1												
Site	Related Participant IDs	Date of Protocol Deviation	Date Protocol Deviation Entered in EDC	Deviation Type	Reason for Protocol Deviation	Related to COVID-19?	Deviation Description	Will Corrective Action be Taken?	Plan to Prevent Recurrence	IRB Reporting Required?	IRB Notified at Continuing Review?	Date of Planned/Actual IRB Report
xxxxxx	xxxxxxxxxxxxxx	mm/dd/yyyy	mm/dd/yyyy	xxxxxxx	xxxxxxx	Yes/No	xxxxxxx	Yes/No	xxxxxxx	Yes/No	Yes/No	mm/dd/yyyy

Major PDs are Highlighted in grey.

Listing 9: Protocol Deviations												
Deviation Category = Category Name 2												
Site	Related Participant IDs	Date of Protocol Deviation	Date Protocol Deviation Entered in EDC	Deviation Type	Reason for Protocol Deviation	Related to COVID-19?	Deviation Description	Will Corrective Action be Taken?	Plan to Prevent Recurrence	IRB Reporting Required?	IRB Notified at Continuing Review?	Date of Planned/Actual IRB Report
xxxxxx	xxxxxxxxxxxxxx	mm/dd/yyyy	mm/dd/yyyy	xxxxxxx	xxxxxxx	Yes/No	xxxxxxx	Yes/No	xxxxxxx	Yes/No	Yes/No	mm/dd/yyyy

Major PDs are Highlighted in grey.

Listing 9: Protocol Deviations

Deviation Category = ...

Site	Related Participant IDs	Date of Protocol Deviation	Date Protocol Deviation Entered in EDC	Deviation Type	Reason for Protocol Deviation	Related to COVID-19?	Deviation Description	Will Corrective Action be Taken?	Plan to Prevent Recurrence	IRB Reporting Required?	IRB Notified at Continuing Review?	Date of Planned/Actual IRB Report
xxxxxxxx	xxxxxxxxxxxxxxxxxx	mm/dd/yyyy	mm/dd/yyyy	xxxxxxxx	xxxxxxxx	Yes/No	xxxxxxxx	Yes/No	xxxxxxxx	Yes/No	Yes/No	mm/dd/yyyy

Major PDs are Highlighted in grey.
